### 15.12.6. Efficacy Figures

Efficacy: Figures					
No.	Population	IDSL / Example Shell	Title	Programming Notes	Deliverable [Priority]
Continuous Efficacy					
2.1.	ITTE	EFF_F01	Forest plot of Observed Mayo Score Change from Baseline	By "Overall" then Advanced Therapy Experience level then by endpoint: Complete, Adapted, Partial (at matching timepoint only). Note: categorical axis shows dose level.	SAC
2.2.	ITTE	EFF_F02	Forest plot of Estimated Difference from Placebo in Mayo Score Change from Baseline	By "Overall" then Advanced Therapy Experience level then by endpoint: Complete, Adapted, Partial (Partial at matching timepoint only). Note: categorical axis shows dose level	SAC
2.3.	IIT_ETP	EFF_F01	Forest plot of Observed Mayo Score Change from Baseline – Extended Treatment Phase	By "Overall" then Advanced Therapy level then panelled by endpoint : Complete, Adapted, Partial (Partial at matching timepoint only). Note: categorical axis shows (both) dose levels	None
2.4.	ITTE	Study 200630, Figure 2.5	Mean ( $\pm$ SE) Plot of Partial Mayo Score over time in induction phase	By dose Page by Absolute and Change from Baseline	SAC
2.5.	IIT_ETP	EFF_F01	Forest plot of Observed UCEIS Total Score – Induction Phase	By "Overall" then Advanced Therapy Experience level Note: categorical axis shows dose level	None

Efficacy: Figures					
No.	Population	IDSL / Example Shell	Title	Programming Notes	Deliverable [Priority]
Categorical Efficacy					
2.6.	ITTE	EFF_F03	Forest plot of Proportions for Categorical Endpoints in Induction Phase - Observed	Panel by Endpoint, then Visit, then Dose. Subgroup (within panel) Advanced Therapy Experience level (Note that proportions / odds ratios are on the same scale across endpoints).	IA3H, SAC
2.7.	ITTE	EFF_F04	Forest Plot for Estimated Response Rates for Categorical Endpoints in Induction Phase	Panel by Endpoint, then Visit, then Dose, then rate/delta. Subgroup (within panel) Advanced Therapy Experience level (Note that proportions / odds ratios are on the same scale across endpoints).  Endoscopic Improvement and Clinical Remission	IA3H, SAC
2.8.	ITTE_ETP	EFF_F03	Forest plot of Observed Proportions for Categorical Endpoints in Extended Treatment Phase	Panel by Endpoint, then Visit, then Dose. Subgroup (within panel) Advanced Therapy Experience level (Note that proportions / odds ratios are on the same scale across endpoints).  Some reporting efforts will not report all endpoints. Footnote: Median and equal tailed credible intervals using non-informative priors in a beta-binomial model.	None

**CONFIDENTIAL**

204869

Efficacy: Figures					
No.	Population	IDSL / Example Shell	Title	Programming Notes	Deliverable [Priority]
2.9.	ITTE	EFF_F03	Forest plot of Proportions for Categorical Endpoints in Induction Phase - Estimands		IA3H, SAC
Daily Diary Scores					
2.10.	ITTE	EFF_F05	Mean (+/-SE) Plot of Daily Diary Scores in Induction Phase	Intervals of 3 days in the x-axis	SAC
2.11.	ITTE	EFF_F06	Plot of Daily Diary Scores for Individual Subjects in Induction Phase - Subgroups	Use the non-rounded versions of derived Rectal Bleeding and Absolute Stool Number  Show patients with Discontinuation and Ulcerative Colitis AEs in induction as a separate groups;  Intervals of 3 days in the x-axis	SAC

### 15.12.7. Safety Tables

Safety: Tables					
No.	Population	IDSL / Example Shell	Title	Programming Notes	Deliverable [Priority]
Adverse Events (AEs)					
3.1.	Safety	AE5A	Summary of All Adverse Events by Intensity, System Organ Class and Preferred Term in Induction Phase	N30: blinded output, do not report treatment group.	N30, SAC
3.2.	Safety	AE1	Summary of All Adverse Events by System Organ Class and Preferred Term in Induction Phase	ICH E3 Add footnote: Note: Onset date of Adverse Event is used to associate AE to study phase.	On request by DRC and SAC
3.3.	Safety ETP	AE5A	Summary of All Adverse Events by Intensity, System Organ Class and Preferred Term in Extended Treatment Phase	Add footnote: Note: Onset date of Adverse Event is used to associate AE to study phase.	On request by DRC and SAC
3.4.	Safety OL I	AE5A	Summary of All Adverse Events by Intensity, System Organ Class and Preferred Term for Open Label Induction Phase	Add footnote: Note: Onset date of Adverse Event is used to associate AE to study phase.	On request by DRC and SAC
3.5.	Safety OL ETP	AE5A	Summary of All Adverse Events by Intensity, System Organ Class and Preferred Term for Open Label Extended Treatment Phase	Add footnote: Note: Onset date of Adverse Event is used to associate AE to study phase.	On request by DRC and SAC
3.6.	Safety	AE3	Summary of Common (>=5%) Adverse Events by Overall Frequency for Induction Phase	Rationale: ICH E3 Add footnote: Note: Onset date of Adverse Event is used to associate AE to study phase.	SAC
3.7.	Safety ETP	AE3	As above for Extended Treatment Phase		None
3.8.	Safety OL I	AE3	As above for Open Label Induction Phase		None
3.9.	Safety OL ETP	AE3	As above for Open Label Extended Treatment Phase		None

Safety: Tables					
No.	Population	IDSL / Example Shell	Title	Programming Notes	Deliverable [Priority]
3.10.	Safety	AE1	Summary All Drug-Related Adverse Events by System Organ Class and Preferred Term for Induction Phase	Rationale: ICH E3 Add footnote: Note: Onset date of Adverse Event is used to associate AE to study phase.	SAC
3.11.	Safety ETP	AE1	As above for Extended Treatment Phase		SAC
3.12.	Safety OL I	AE1	As above for Open Label Induction Phase		SAC
3.13.	Safety OL ETP	AE1	As above for Open Label Extended Treatment Phase		SAC
3.14.	Safety	AE15	Summary of Common (>=5%) Non-serious Adverse Events by System Organ Class and Preferred Term (Number of Subjects and Occurrences) for Induction Phase	Rationale: disclosure for FDAAA, EudraCT Add footnote: Note: Onset date of Adverse Event is used to associate AE to study phase.	SAC
3.15.	Safety ETP	AE15	Summary of Non-serious Adverse Events by System Organ Class and Preferred Term (Number of Subjects and Occurrences) for Extended Treatment Phase		SAC
3.16.	Safety OL I	AE15	As above for Open Label Induction Phase		SAC
3.17.	Safety OL ETP	AE15	As above for Open Label Extended Treatment Phase		SAC
Serious and Other Significant Adverse Events					
3.18.	Safety	AE16	Blinded summary of Serious Adverse Events by System Organ Class and Preferred Term (Number of Subjects and Occurrences) for Induction Phase	This is a blinded output, do not report treatment group.	N30

Safety: Tables					
No.	Population	IDS / Example Shell	Title	Programming Notes	Deliverable [Priority]
3.19.	Safety	AE16	Summary of Serious Adverse Events by System Organ Class and Preferred Term (Number of Subjects and Occurrences) for Induction Phase	Rationale: disclosure for FDAAA, EudraCT Add footnote: Note: Onset date of Adverse Event is used to associate AE to study phase.	SAC
3.20.	Safety ETP	AE16	As above for Extended Treatment Phase		SAC
3.21.	Safety OL I	AE16	As above for Open Label Induction Phase		SAC
3.22.	Safety OL ETP	AE16	As above for Open Label Extended Treatment Phase		SAC
3.23.	Safety	AE3	Summary of Adverse Events Leading to Permanent Discontinuation of Study Treatment or Withdrawal from Study by Overall Frequency for Induction Phase	IDS Add footnote: Note: Onset date of Adverse Event is used to associate AE to study phase.	SAC
3.24.	Safety ETP	AE3	As above for Extended Treatment Phase		None
3.25.	Safety OL I	AE3	As above for Open Label Induction Phase		None
3.26.	Safety OL ETP	AE3	As above for Open Label Extended Treatment Phase		None
Laboratory: Chemistry					
3.27.	Safety	LB1	Summary of Chemistry Changes from Baseline for Induction Phase	Rationale: ICH E3	SAC
3.28.	Safety ETP	LB1	As above for Extended Treatment Phase	Rationale: ICH E3	SAC
3.29.	Safety OL I	LB1	As above for Open Label Induction Phase	Rationale: ICH E3	SAC

Safety: Tables					
No.	Population	IDS / Example Shell	Title	Programming Notes	Deliverable [Priority]
3.30.	Safety OL ETP	LB1	As above for Open Label Extended Treatment Phase	Rationale: ICH E3	SAC
3.31.	Safety	LB17	Summary of Worst-Case Chemistry Results by PCI Criteria Post-Baseline Relative to Baseline for Induction Phase	Rationale: ICH E3 and disclosure	SAC
3.32.	Safety ETP	LB17	Summary of Worst-Case Chemistry Results by PCI Criteria Post-Baseline Relative to Baseline for Extended Treatment Phase	Rationale: ICH E3 Footnote: "Note: Induction phase baseline used"	SAC
3.33.	Safety OL I	LB17	Summary of Worst-Case Chemistry Results by PCI Criteria Post-Baseline Relative to Baseline for Open Label Induction Phase	Rationale: ICH E3 Footnote: "Note: Induction phase baseline used"	SAC
3.34.	Safety OL ETP	LB17	Summary of Worst-Case Chemistry Results by PCI Criteria Post-Baseline Relative to Baseline for Open Label Extended Treatment Phase	Rationale: ICH E3 Footnote: "Note: Induction phase baseline used"	SAC
Laboratory: Haematology					
3.35.	Safety	LB1	Summary of Haematology Changes from Baseline for Induction Phase	Rationale: ICH E3	SAC
3.36.	Safety ETP	LB1	As above for Extended Treatment Phase	Rationale: ICH E3	SAC
3.37.	Safety OL I	LB1	As above for Open Label Induction Phase	Rationale: ICH E3	SAC
3.38.	Safety OL ETP	LB1	As above for Open Label Extended Treatment Phase	Rationale: ICH E3	SAC

Safety: Tables					
No.	Population	IDS / Example Shell	Title	Programming Notes	Deliverable [Priority]
3.39.	Safety	LB17	Summary of Worst-Case Haematology Results by PCI Criteria Post-Baseline Relative to Baseline for Induction Phase	Rationale: ICH E3 and disclosure	SAC
3.40.	Safety ETP	LB17	Summary of Worst-Case Haematology Results by PCI Criteria Post-Baseline Relative to Baseline for Extended Treatment Phase	Rationale: ICH E3 Footnote: "Note: Induction phase baseline used"	SAC
3.41.	Safety OL I	LB17	Summary of Worst-Case Haematology Results by PCI Criteria Post-Baseline Relative to Baseline for Open Label Induction Phase	Rationale: ICH E3 Footnote: "Note: Induction phase baseline used"	SAC
3.42.	Safety OL ETP	LB17	Summary of Worst-Case Haematology Results by PCI Criteria Post-Baseline Relative to Baseline for Open Label Extended Treatment Phase	Rationale: ICH E3 Footnote: "Note: Induction phase baseline used"	SAC
Laboratory: Urinalysis					
3.43.	Safety	UR1	Summary of Worst-Case Urinalysis Results by PCI Criteria Post-Baseline Relative to Baseline for Induction Phase	ICH E3	SAC
3.44.	Safety ETP	UR1	Summary of Worst-Case Urinalysis Results by PCI Criteria Post-Baseline Relative to Baseline for Extended Treatment Phase	ICH E3	SAC
3.45.	Safety OL I	UR1	Summary of Worst-Case Urinalysis Results by PCI Criteria Post-Baseline Relative to Baseline for Open Label Induction Phase	ICH E3	SAC
3.46.	Safety OL ETP	UR1	Summary of Worst-Case Urinalysis Results by PCI Criteria Post-Baseline Relative to Baseline for Open Label Extended Treatment Phase	ICH E3	SAC

Safety: Tables					
No.	Population	IDS / Example Shell	Title	Programming Notes	Deliverable [Priority]
ECG					
3.47.	Safety	EG1	Summary of ECG Findings for Induction Phase	IDS	SAC
3.48.	Safety ETP	EG1	As above for Extended Treatment Phase		SAC
3.49.	Safety OL I	EG1	As above for Open Label Induction Phase		SAC
3.50.	Safety OL ETP	EG1	As above for Open Label Extended Treatment Phase		SAC
3.51.	Safety	EG2	Summary of Change from Baseline in ECG Values by Visit for Induction Phase		None
3.52.	Safety ETP	EG2	As above for Extended Treatment Phase		None
3.53.	Safety OL I	EG2	As above for Open Label Induction Phase		None
3.54.	Safety OL ETP	EG2	As above for Open Label Extended Treatment Phase		None
3.55.	Safety	EG10	Summary of Maximum QTc Values Post-Baseline Relative to Baseline by Category for Induction Phase	IDS	SAC
3.56.	Safety ETP	EG10	As above for Extended Treatment Phase	Footnote: "Note: Induction phase baseline used"	SAC
3.57.	Safety OL I	EG10	As above for Open Label Induction Phase	Footnote: "Note: Induction phase baseline used"	SAC
3.58.	Safety OL ETP	EG10	As above for Open Label Extended Treatment Phase	Footnote: "Note: Induction phase baseline used"	SAC
3.59.	Safety	EG11	Summary of Maximum Increase in QTc Values Post-Baseline Relative to Baseline by Category for Induction Phase	Rationale: disclosure IDS	SAC

Safety: Tables					
No.	Population	IDS / Example Shell	Title	Programming Notes	Deliverable [Priority]
3.60.	Safety ETP	EG11	As above for Extended Treatment Phase	Footnote: "Note: Induction phase baseline used"	SAC
3.61.	Safety OL I	EG11	As above for Open Label Induction Phase	Footnote: "Note: Induction phase baseline used"	SAC
3.62.	Safety OL ETP	EG11	As above for Open Label Extended Treatment Phase	Footnote: "Note: Induction phase baseline used"	SAC
Vital Signs					
3.63.	Safety	VS1	Summary of Change from Baseline in Vital Signs for Induction Phase	ICH E3	SAC
3.64.	Safety ETP	VS1	As above for Extended Treatment Phase		SAC
3.65.	Safety OL I	VS1	As above for Open Label Induction Phase		SAC
3.66.	Safety OL ETP	VS1	As above for Open Label Extended Treatment Phase		SAC
3.67.	Safety	VS7	Summary of Worst-Case Vital Signs Results by PCI Criteria Post-Baseline Relative to Baseline for Induction Phase	IDS Note: Adjust shell to include temperature (required for disclosure). Use footnote and title of middle category from VS7 (i.e. change 'normal' to 'within range') Include change from baseline for Systolic Blood Pressure, Diastolic Blood Pressure and Heart Rate	SAC
3.68.	Safety ETP	VS7	As above for Extended Treatment Phase		SAC
3.69.	Safety OL I	VS7	As above for Open Label Induction Phase		SAC

Safety: Tables					
No.	Population	IDSL / Example Shell	Title	Programming Notes	Deliverable [Priority]
3.70.	Safety OL ETP	VS7	As above for Open Label Extended Treatment Phase		SAC
Immunogenicity					
3.71.	Safety	sb240563/mid20 5050/final_02/ Table 3.38	Summary of Confirmed Positive Binding Antibody by Visit for Induction Phase		SAC
3.72.	Safety ETP	sb240563/mid20 5050/final_02/ Table 3.38	As above for Extended Treatment Phase		SAC
3.73.	Safety OL I	sb240563/mid20 5050/final_02/ Table 3.38	As above for Open Label Induction Phase		SAC
3.74.	Safety OL ETP	sb240563/mid20 5050/final_02/ Table 3.38	As above for Open Label Extended Treatment Phase		SAC
3.75.	Safety	sb240563/mid20 5050/final_02/ Table 3.39	Summary of Confirmed Positive Neutralising Antibody by Visit for Induction Phase		None

Safety: Tables					
No.	Population	IDSL / Example Shell	Title	Programming Notes	Deliverable [Priority]
3.76.	Safety ETP	sb240563/mid20 5050/final_02/ Table 3.39	As above for Extended Treatment Phase		None
3.77.	Safety OL I	sb240563/mid20 5050/final_02/ Table 3.39	As above for Open Label Induction Phase		None
3.78.	Safety OL ETP	sb240563/mid20 5050/final_02/ Table 3.39	As above for Open Label Extended Treatment Phase		None
Adverse Events – Additional Summaries					
3.79.	Safety	AE17	Summary of Exposure Adjusted Incidence Rates for Adverse Events in Induction Phase	For selected Preferred Terms – 1) All Preferred terms in System Organ class of Infections and Infestations 2) Preferred Term – Colitis Ulcerative	SAC
3.80.	Safety	TTE1	Summary of Time to Ulcerative Colitis Adverse Event in Induction Phase	For selected Preferred Terms – 1) Preferred Term – Colitis Ulcerative	SAC

Safety: Tables					
No.	Population	IDSL / Example Shell	Title	Programming Notes	Deliverable [Priority]
COVID-19 Pandemic Impact					
3.81.	Safety	PAN4	Summary of COVID-19 Pandemic Visit Impacts		SAC

### 15.12.8. Safety Figures

Safety: Figures					
No.	Population	IDSL / Example Shell	Title	Programming Notes	Deliverable [Priority]
Adverse Events					
3.1.	Safety	AE10	Plot of Common (>=5%) Adverse Events for Induction Phase	
Incidence <math>\geq 5\%</math> on either active or placebo
 
Separate page for each treatment compared to placebo; plus combined treatment compared to placebo
 
Add following footnote and use in programming rules:
 
“Note: All displayed Adverse Events (AEs) have occurrence <math>\geq 5\%</math> in an active treatment group and the AE has to have at least 1 occurrence in the placebo group for relative risk to be calculated. Only AEs with calculated relative risk are displayed.”
	SAC
Hepatobiliary (Liver)					
3.2.	Safety	LIVER14	Scatter Plot of Maximum vs. Baseline for ALT for Induction Phase		SAC
3.3.	Safety_ETP	LIVER14	Scatter Plot of Maximum vs. Baseline for ALT for Extended Treatment Phase	Footnote: “Note: Induction phase baseline used”	None
3.4.	Safety_DL_I	LIVER14	Scatter Plot of Maximum vs. Baseline for ALT for Open Label Induction Phase	Footnote: “Note: Induction phase baseline used”	None
3.5.	Safety_DL_ETP	LIVER14	Scatter Plot of Maximum vs. Baseline for ALT for Open Label Extended Treatment Phase	Footnote: “Note: Induction phase baseline used”	None

Safety: Figures					
No.	Population	IDSL / Example Shell	Title	Programming Notes	Deliverable [Priority]
3.6.	Safety	LIVER9	Scatter Plot of Maximum ALT vs. Maximum Total Bilirubin for Induction Phase		SAC
3.7.	Safety_ETP	LIVER9	Scatter Plot of Maximum ALT vs. Maximum Total Bilirubin for Extended Treatment Phase		None
3.8.	Safety_DL_I	LIVER9	Scatter Plot of Maximum ALT vs. Maximum Total Bilirubin for Open Label Induction Phase		None
3.9.	Safety_DL_ETP	LIVER9	Scatter Plot of Maximum ALT vs. Maximum Total Bilirubin for Open Label Extended Treatment Phase		None

### 15.12.9. Pharmacokinetic Tables

Pharmacokinetic: Tables					
No.	Population	IDSL / Example Shell	Title	Programming Notes	Deliverable [Priority]
PK concentration					
4.1.	PK	PKCT1	Summary of Plasma GSK2831781 Concentration-Time Data (ng/mL) for Induction Phase	Note: LLQ=10 ng/mL. SE and 95% CI (Lower, Upper) are set to missing if No. Imputed/n > 0.3.	SAC
4.2.	PK_ETP	PKCT1	Summary of Plasma GSK2831781 Concentration-Time Data (ng/mL) in Extended Treatment Phase	Note: LLQ=10 ng/mL. SE and 95% CI (Lower, Upper) are set to missing if No. Imputed/n > 0.3. Programming note: data should be summarised by dose group of Induction Phase	SAC
4.3.	PK_OL	PKCT1	Summary of Plasma GSK2831781 Concentration-Time Data (ng/mL) in Open Label Induction Phase by Double Blind Induction Treatment	Note: LLQ=10 ng/mL. SE and 95% CI (Lower, Upper) are set to missing if No. Imputed/n > 0.3. Please add a note: "Note that subjects had different doses during the Induction Phase"	SAC
4.4.	PK_OL_ETP	PKCT1	Summary of Plasma GSK2831781 Concentration-Time Data (ng/mL) in Open Label Extended Treatment Phase by Double Blind Induction Treatment	Note: LLQ=10 ng/mL. SE and 95% CI (Lower, Upper) are set to missing if No. Imputed/n > 0.3.	SAC
PK derived parameters					
4.5.	PK_ETP	PK03	Summary of derived plasma GSK2831781 pharmacokinetic parameters in Extended Treatment Phase (SC dosing)		SAC

Pharmacokinetic: Tables					
No.	Population	IDSL / Example Shell	Title	Programming Notes	Deliverable [Priority]
4.6.	PK_ETP	PK05	Summary of log-transformed derived plasma GSK2831781 pharmacokinetic parameters in Extended Treatment Phase (SC dosing)		SAC

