
 To evaluate the safety and tolerability of repeat doses of GSK2831781 during the Double-Blind Extended Treatment Phase. 	
 Incidence of adverse events and serious adverse events in the Double-Blind Extended Treatment Phase. Incidence of findings of potential clinical importance during the Double-Blind Extended Treatment Phase for: 
 Vital signs Clinical laboratory values (haematology, clinical chemistry and urinalysis). QTc.

 To investigate the effect of repeat doses of GSK2831781 on clinical efficacy including endoscopic mucosal healing during the Double-Blind Induction Phase. 	
 Adapted Mayo endoscopic score of 0 or 1 at Week 10. Adapted Mayo clinical remission³ at Week 10. Adapted Mayo clinical response³ at Week 10. Symptomatic remission⁴ over time. Change from baseline in Partial Mayo score over time. Change from baseline in Adapted Mayo endoscopic score and Ulcerative Colitis Endoscopic Index of Severity (UCEIS) at Week 10.

 To investigate the effect of repeat doses of GSK2831781 on UC histologic disease activity during the Double-Blind Induction Phase. 	
 Histological severity as determined by the Robarts Histopathology Index at Week 10. Histological severity as determined by the Nancy Histological Index at Week 10. Histological severity as determined by the Geboes Histological Index at Week 10.

 To investigate the effect of repeat doses of GSK2831781 on biomarkers of UC disease activity during the Double-Blind Induction Phase. 	
 Change from baseline in serum C-reactive protein over time. Change from baseline in faecal calprotectin over time.

 To investigate the pharmacokinetics of GSK2831781 following subcutaneous dosing. 	
 GSK2831781 PK parameters: AUC(0-tau), Cmax, tmax.

Objectives	Endpoints

 To investigate the immunogenicity of repeat doses of GSK2831781 during the Double-Blind Induction Phase. 	
 Incidence of anti-drug antibodies at each visit.
Safety	

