1.2. Schema

*Randomisation will initially be 2:1 to GSK2831781 450 mg or Placebo. When an appropriate number of participants have been randomised in these two arms for the interim analysis (Interim Analysis 3, see Section 9.5), randomisation to all dose regimens (GSK2831781 450 mg, 300 mg 150 mg, 45 mg or placebo) will be opened at a ratio of 2:3:3:3:2.. Dosing during the Double-Blind Induction Phase will be undertaken at Weeks 0 (Day 1), 2, 6 and 10. Responders at Week 10 (where Responder status is determined by a pre-specified algorithm in the eCRF) will continue into the Double-Blind ETP.

Participants originally randomised to GSK2831781 IV treatment arms (Induction) will receive subcutaneous doses of 300 mg GSK2831781 every 4 weeks at Weeks 14, 18, 22, and 26. Participants originally on placebo treatment arm, who attained response, will continue to receive blinded placebo through SC dosing at Weeks 14, 18, 22 and 26. The Double-Blind ETP ends at Week 30, with Follow-Up until Week 42 (16 weeks after the last dose).

[†]The open label patient journey is described fully in Section 4.1.2 and [Figure 3](#). The Open Label ETP, for Non-Responders at Week 10, will constitute a full 10 weeks of induction dosing according to the same dosing schedule as GSK2831781 450 mg (IV doses at Weeks 12, 14, 18 and 22). The Open Label Induction Phase (OLIP) will start at Week 12 to allow turnaround of centrally determined responder status. Response following OLIP will be assessed at Week 22 in the Open Label ETP, and Responders will continue with doses of 300 mg GSK2831781 subcutaneously every 4 weeks from Week 26 to 38. Participants will then undertake a Follow-Up period of 12 weeks from Week 42 to Week 54. Participants in the Open Label ETP who are Non-Responders at Week 22 will discontinue study treatment and be managed according to physician standard of care but are still required to attend a Follow-Up visit approximately 16 weeks from the last dose event.

1.3. Schedule of Activities (SoA):

Double-Blind Treatment SoA

WEEK	Screening		Induction Phase					Extended Treatment Phase					Follow-Up ²⁰	Early Withdrawal Visit ^{21, 26}		
	Pre-dose	Post-dose	2	4 ²⁶	6	10	12 ¹⁹	14	18 ²⁶	22 ²⁶	26 ²⁶	30	42 ²⁶			
DAY	-35 to -7 ²³	-14 to -7 ¹⁴	Day 1		15	29	43	71	85	99	127	155	183	211	295	
Window (days)					±2	±3	±3	±3	±5	±3	±3	±3	±3	±3	±7	
Study Population																
Informed Consent	X															
Inclusion/Exclusion Criteria	X															
Demography	X															

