- 2 Endoscopy should be flexible sigmoidoscopy. However, colonoscopy can be performed at screening if required for assessment of dysplasia risk (see Section 5.1), and at any timepoint if clinically indicated.
- 3 ECG in triplicate at screening and single at all other time points. See Section 8.6.3, Electrocardiograms for further detail.
- 4 Collection of SAEs starts from screening whilst collection of AEs will commence from Day 1.
- 5 Unless specified otherwise, all samples will be taken prior to administration of study treatment.
- 6 Negative test required during screening and immediately prior to the first dose of study treatment. A serum pregnancy test is required at screening, after which a highly sensitive urine pregnancy test is adequate. If a urine test cannot be confirmed as negative, a serum pregnancy test is required.
- 7 A PPD test maybe performed following two indeterminate Quantiferon tests to determine TB status, see Section 5.2.
- 8 To confirm postmenopausal status, serum FSH and oestradiol testing will be performed for all postmenopausal females at the screening visit.
- 9 See Section 6.2 for details of dosing duration and monitoring period.
- 10 Unless stated, samples taken on a day of dosing must be pre-dose sample (up to 2 hr before the next dose).
- 11 Additional sampling will be required in a subset of participants to characterise SC pharmacokinetics. See Section 8.3, for schedule.
- 12 LAG3 depletion will only be undertaken in sites where shipping to central lab can be achieved in the required timeframe, see Section 8.4, and SRM.
- 13 IBDQ, FACIT-Fatigue, SF-36, PGIC and PGIS are to be performed before any other assessments on visit days.
- 14 A 7-day window enables turnaround of centrally read endoscopy score for inclusion to arrange Day 1 visit; however, endoscopy can be performed up to Day -3 if all other criteria for study eligibility have been met by this time and Robarts have agreed rapid turnaround of central endoscopy read.
- 15 PGIC not to be done on Day 1.
- 16 Vital signs to be taken every 30 minutes (\pm 5 minutes) until completion of post dose monitoring period. A single ECG be taken within 4 hours of completion of dose administration. For participants who have discontinued treatment but remain on study, post-dose monitoring does not apply.
- 17 Samples to be taken immediately after end of IV infusion (preferably within 15 minutes).

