8.3. Pharmacokinetics

Blood samples for pharmacokinetic analysis of GSK2831781 will be collected at the time points indicated in Section 1.3, for all participants.

In order to properly characterise subcutaneous bioavailability and PK, additional subcutaneous PK and sLAG3 sampling will be performed on a subset of participants. The additional samples will be taken according to one of two schedules ([Table 5](#) and [Table 6](#)), determined in discussion with the Sponsor or their representative and the study site. Once samples have been collected for a sufficient number of participants, this sampling may be discontinued, at the discretion of the Sponsor. The actual date and time of each blood sample collection will be recorded. The timing of PK samples may be altered and/or PK samples may be obtained at additional time points to ensure thorough PK monitoring. Collection, sample handling, processing, storage and shipping procedures are provided in the SRM or equivalent.

For details on home healthcare approaches, please refer to [Appendix 10](#).

Table 5 SC PK and sLAG3 characterisation schedules for selected participants – Schedule 1

Week	14		15
Days since first SC dose	1	3	7
PK	X	X	X
sLAG3	X	X	X

Footnote: Samples can be taken at any time on the day

Table 6 SC PK and sLAG3 characterisation schedules for selected participants – Schedule 2

Week	14		15
Days since first SC dose	2	5	10
PK	X	X	X
sLAG3	X	X	X

Footnote: Samples can be taken at any time on the day

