##### 11.1.1.2. Derived Pharmacokinetic Parameters

Pharmacokinetic parameters will be calculated by standard non-compartmental analysis of PK concentration according to current working practices and using the currently supported version of WinNonlin (version 6.3 or higher). All calculations of non-compartmental parameters will be based on actual sampling times. Pharmacokinetic parameters listed will be determined from the plasma concentration-time data, as data permits.

Parameter	Parameter Description
AUC(0-tau)	Area under the concentration curve to the end of the dosing period
Cmax	Maximum concentration observed
tmax	Time at which the maximum concentration Cmax is observed

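### SC pharmacokinetic Tables 4.5 and 4.6 include drug left from IV induction, so they overstate exposure from the 300 mg SC dose itself by an amount that depends on induction dose

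*SAP*

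**What the plan says.** **Objective.** A secondary objective is "To investigate the pharmacokinetics of GSK2831781 following subcutaneous dosing", with endpoints AUC(0-tau), Cmax and tmax (Protocol 1.1 and 3; SAP 2.2).

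**Dosing.** Protocol 1.2: "Dosing during the Double-Blind Induction Phase will be undertaken at Weeks 0 (Day 1), 2, 6 and 10". Week 10 responders from the active arms then receive "subcutaneous doses of 300 mg GSK2831781 every 4 weeks at Weeks 14, 18, 22, and 26".

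**Sampling.** Protocol 8.3 adds post-dose SC samples in a subset. Tables 5 and 6 index them by "Days since first SC dose": days 1, 3 and 7, or days 2, 5 and 10. At other dosing visits, footnote 10 of the Schedule of Activities (Protocol 1.3) says that "samples taken on a day of dosing must be pre-dose sample (up to 2 hr before the next dose" unless stated otherwise.

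**Derivation.** SAP 11.1.1.2 applies standard non-compartmental analysis (NCA) to PK concentration and defines AUC(0-tau) as "Area under the concentration curve to the end of the dosing period". It names no SC dose and describes no adjustment for the pre-dose level.

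**Display.** SAP 11.1.4 summarises PK endpoints by treatment, and SAP 5.1.1 gives the four active induction sequences one extended-phase label, 300 mg SC. In SAP 15.12.9, the note to concentration Table 4.2 says "data should be summarised by dose group of Induction Phase", and the titles of Tables 4.3 and 4.4 specify double-blind induction treatment. Parameter Tables 4.5 ("Summary of derived plasma GSK2831781 pharmacokinetic parameters in Extended Treatment Phase (SC dosing") and 4.6 have no such note.

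**Model.** SAP 12 and 15.9.2 plan a population PK model with linear and non-linear elimination, extended to SC absorption, with disposition assumed the same for both routes.

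**The concern.** Only the Week 14 to 18 interval has post-dose SC samples, so it is the only one from which Cmax, tmax and AUC(0-tau) can properly be derived. Every active participant who reaches it on schedule had an IV dose of 45 to 450 mg four weeks earlier. NCA of total concentration attributes whatever remains of that drug to the SC interval.

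Protocol 4.2 says that the SC phase should show whether this route is applicable in future studies, and Protocol 8.3 says that the extra samples are meant to characterise SC bioavailability. A pooled AUC or Cmax containing an unstated share of IV drug does not answer either question. The SAP treats induction dose as relevant to the concentrations but drops it for the parameters computed from them. SAP 2.1.4 and 2.4 expect few participants on the three middle doses, so the pooled group would be mainly ex-450 mg, where the residue is largest.

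**Working it through.** The documents give no Week 14 residue, SC bioavailability or SC AUC, so there is no stated figure to reproduce. The residue can be bracketed from their IV figures.

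1. **Gap.** Week 14 is Day 99 and Week 10 is Day 71: 99 − 71 = 28 days.

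2. **Elimination rate k, two anchors, one compartment.**
   - A: Protocol 4.3.1 predicts, at Week 10 on 450 mg, Cmax 204 µg/mL and AUC over 4 weeks of 37 mg.hr/mL, which is 37 × 1000/24 = 1,541.7 µg.day/mL. Solving 204/k × (1 − e^(−28k)) = 1,541.7 gives k = 0.1287/day, half-life 5.4 days.
   - B: Protocol 4.2 reports a fall from 162 to 0.5 µg/mL over 12 weeks after 5 mg/kg. k = ln(162/0.5)/84 = 0.0688/day, half-life 10.1 days. The mean dose was 5 × 94.38 = 471.9 mg, so the starting level for 450 mg is 162 × 450/471.9 = 154.5 µg/mL.

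3. **Residue just before the first SC dose, 450 mg arm.** The four IV doses were given 28, 56, 84 and 98 days earlier. Residue = C0 × Σe^(−kx).
   - A: 204 × 0.0280 = 5.7 µg/mL.
   - B: 154.5 × 0.1711 = 26.4 µg/mL.
   - A biexponential cross-check gives 15.6 µg/mL from the last dose alone, between the two.

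4. **Residual AUC over Weeks 14 to 18** = residue/k × (1 − e^(−28k)).
   - A: 5.7/0.1287 × 0.9728 = 43.1 µg.day/mL; × 24/1000 = 1.03 mg.hr/mL.
   - B: 26.4/0.0688 × 0.8544 = 328 µg.day/mL; × 24/1000 = 7.9 mg.hr/mL.

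5. **SC dose alone.** C(t) = F × 300 × (C0/450) × ka/(ka − k) × (e^(−kt) − e^(−ka·t)), with assumed F = 0.5 to 0.8 and ka = 0.2 to 0.5/day. AUC(0-28 d) is 11.8 to 19.5 mg.hr/mL under A and 14.0 to 23.9 under B. Cmax is 30.7 to 68.0 and 29.4 to 60.0 µg/mL respectively.

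6. **AUC factor = (SC + residue)/SC, after 450 mg.**
   - A: (11.8 + 1.03)/11.8 = 1.09, down to (19.5 + 1.03)/19.5 = 1.05.
   - B: (14.0 + 7.9)/14.0 = 1.56, down to (23.9 + 7.9)/23.9 = 1.33.
   - Cmax factors have the same ranges.

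7. **All induction doses.** Under linear kinetics the residue scales with dose. The last column compares the Week 14 to 18 value with simulated steady-state 300 mg SC every 4 weeks.

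| Induction dose | AUC and Cmax relative to SC dose alone | Relative to SC steady state |
|---|---|---|
| 450 mg | 1.05–1.56 | 0.98–1.27 |
| 300 mg | 1.04–1.37 | 0.96–1.12 |
| 150 mg | 1.02–1.19 | 0.87–0.99 |
| 45 mg | 1.01–1.06 | 0.81–0.97 |

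8. **tmax.** The residue is falling while the SC dose is absorbed, so the peak of the total comes earlier than the peak of the SC dose alone. That shift is not sized here.

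**The case against.** **The target exposure is never stated.** In a regimen of IV induction followed by SC dosing, total concentration over a dosing interval is a legitimate quantity, and against steady state the low-dose groups would be understated. This stands: an overstatement can be claimed only relative to the SC dose itself. But bioavailability, the stated purpose of the extra sampling, is about what that dose delivers. If steady state was meant, one pooled first-dose figure does not give it either.

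**Separating IV from SC drug is already planned.** The population PK model uses the full dosing history. Table 4.2 shows concentrations by induction dose, and Listings 53 and 54 give individual data. This stands in part and points to the remedy. However, the model is reported separately from the main study report (SAP 12.1), does not feed Tables 4.5 and 4.6, and has no listed table of SC AUC or Cmax. Figures 4.1, 4.3 and 4.4, where carry-over could be seen, are no longer deliverables.

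**A split would change little.** With few participants on the middle doses, most columns would be nearly empty. This stands, so the split alone is not enough.

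**The NCA guidance and table shells are not in the documents.** A correction or column layout there cannot be excluded and should be confirmed.

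**Conclusion.** The concern holds in a limited form. As written, the plan reports first-dose SC parameters that contain IV residue, pooled over induction doses. Relative to exposure from the 300 mg SC dose alone, they are too high for every active-induction participant who still has IV drug on board: illustratively 5% to 56% after 450 mg and 1% to 6% after 45 mg. These figures rest on linear one-compartment kinetics and on assumed bioavailability and absorption rate. The protocol describes the kinetics as non-linear, so they indicate scale only.

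Two stronger readings are not supported. A reader might infer that SC exposure is roughly doubled or worse. Taking clearance as 450/37 with half-lives of 14 and 18 days does give AUC factors of 2.08 and 2.68 at bioavailability 0.5. But those half-lives would leave 162 × 2^(−84/14) = 2.5 and 162 × 2^(−84/18) = 6.4 µg/mL at 12 weeks, against 0.5 reported, and they imply a Week 10 Cmax of 103 and 90 µg/mL against 204 predicted. A reader might also infer that the tables are overstated whatever the comparator. Against steady-state SC exposure, the ex-150 mg and ex-45 mg values fall below it and the ex-450 mg values lie on either side.

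**What to change.** In SAP 11.1.1.2 and Tables 4.5 and 4.6:

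- State that the parameters refer to the first SC dose (Weeks 14 to 18) and to total concentration.
- Present them by induction dose group, as in Table 4.2, with the Week 14 pre-dose concentration alongside.
- Add a footnote that the values include IV carry-over.
- Take conclusions on SC-dose AUC(0-tau), Cmax and bioavailability from the planned population PK model, which accounts for IV dosing history and non-linear elimination. Add the corresponding model-based output.

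Do not correct the NCA values by subtracting a decayed Week 14 level. SAP 15.9.2 specifies target-mediated and Michaelis-Menten elimination, so residual and SC drug share a saturable pathway and simple subtraction is not valid.

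The cost is SAP wording, two re-programmed tables and one further model output, with no new samples. The SC exposure conclusion becomes model-based, and some induction-dose columns will be sparse.
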